Self-Report Measures and Assessor Ratings: No risks are seen associated with these assessment procedures other than discomfort associated with the recording. These will be handled as described above for recording of assessment and BFI sessions.

Clinician Data: The major types of risk stemming from study participation include the discomfort of revealing personal information and opinions during surveys or interviews, and an unforeseen breach of confidentiality, which could affect employment. Every effort will be made to minimize this risk. Providers who participate will experience risks associated with the evaluations and monitoring of the effects of training on their ability to use the BFI. The major types of risk stemming from study participation include: the discomfort of revealing personal information on the surveys or interviews and discomfort at having their in-session behaviors evaluated and monitored to assess their ability to adhere to the protocol.

2. Adequacy of Protection Against Risks

a. Recruitment and consent procedures

Following the recruitment procedures used in recent clinical trials within BSD, we plan to recruit participants from various specialty clinics at VABHS. Patients will be recruited in these clinics by providing clinic staff and directors information about the study and placing study advertisements around VABHS. A recent PTSD trial using this technique was able to randomize 3 participants per month. Given that the criteria are not very stringent for the proposed study, we expect a good flow of recruitment. The study announcements will state that the free family intervention is part of a research study that is available to qualified individuals. Interested individuals will be instructed to call for further information.

In accordance with HIPAA regulations, written informed consent will be obtained from each participant after a thorough explanation of procedures by a project staff person and the opportunity for the participant to ask and receive answers to questions. Participants will be informed of the nature of the investigation, the types of assessments and treatments involved, alternative treatments, and the potential risks involved in participation and will be asked to sign an informed consent statement prior to participating in the proposed study. In addition, the participant will receive an explanation of how information related to their case will be handled including all parties involved, data management, and plans to publish data in group format without identifying information. Participants will also be informed that if suicidal intentions are disclosed confidentiality may be broken in order for protective measures to be taken. See Section 5 (Data Safety and Monitoring Plan) for specific information on assessment of suicidal information from participants and at what point action(s) would be taken.

To prevent clinic staff from feeling pressure to participate, the following measures will be taken: Several clinics that commonly treat PTSD (e.g., the PTSD Clinical Team, Women's Stress Disorders Treatment Team, General Mental Health, Center for Returning Veterans) and employ multiple clinicians (more than 5) will be contacted at the time of recruitment and informed of the option to participate. It will be made clear that surveys and interviews assessing information that is gathered during the study will not be shared with the administration (other than in the prepared research report, which will not disclose participant name or identifying characteristics). Providers who participate will receive a thorough description of study-related procedures, will have the opportunity to ask questions, and will provide informed consent. Providers who participate by providing the intervention, and/or completing surveys and interviews all will be asked to provide informed consent. Interview, survey responses, and competence and adherence data collected will not be made available to employers or become a part of their employment records and will remain confidential.

b. Protection against risk

1. We will carefully screen to identify individuals whose risk for potential adverse outcomes is elevated were they to participate in the proposed research. Such individuals will be excluded from the study. As an

example, an actively suicidal person would be excluded from study participation and appropriate clinical treatment or referrals provided.

2. Clinical staff will be trained to cope with any anxiety/distress experienced by participants during the assessments and intervention. Staff will also monitor assessment items that ask about risk of suicide or current domestic violence at each timepoint. These items will be reviewed immediately upon completion, and participants who endorse elevated risk of suicide or current domestic violence will meet with the PI for further assessment. See Section 5b ("Safety monitoring plan") below for details of the standard procedure for suicidal risk. For current domestic violence, the PI (in consultation with a licensed clinical supervisor on site) will assess risk and provide the participant with clinical and community referrals as needed.

3. Careful monitoring of participants during study participation will be conducted by the project staff. Participants will be monitored for any increase in symptoms as the study progresses. Each participant will see the same clinician for each of their treatment or intervention visits (in the case of Veterans, their same usual care clinician. In the case of family members, the same BFI clinician), and the same assessor for each assessment occasion when appropriate. Following the clinical trial policy of the VA Boston Healthcare System, all participants will be given an emergency number to call in case of an emergency. This number will be the psychiatry on call system of the VA Boston Healthcare System.

4. Participants will be instructed to contact study personnel at any time (including during the follow-up period) in the event of worsening symptoms. Participants whose clinical condition has deteriorated will be removed from the study and given appropriate clinical care. See DSMP for details.

5. Veterans will be under treatment with clinicians at the VA Boston Healthcare System, and thus will be monitored by their clinicians and will be provided with appropriate referrals as necessary at the end of their PTSD treatment. Family members failing to benefit from the study intervention will be provided with appropriate clinical care and referrals. The exact nature of these referrals will be determined by the judgment of clinicians and supervisor familiar with the specific participant and may include services delivered by the Social Work Service of VA Boston or other community resources.

6. As in any type of treatment or clinical research program, participants' (those receiving interventions and all clinician participants) confidentiality must be carefully guarded and respected. All data with identifying information will be stored in locked files or password-protected computer servers. Data being analyzed will be identified by subject codes, and identifying information will be removed. The identity of participants will not be revealed in the presentation or publication of any results from the project. All personnel working on the project will be educated about the importance of strictly respecting participants' rights to confidentiality and will have completed several training courses including proper practice in accordance with HIPAA regulations, protection of human subjects, and computer security.

3. Potential Benefits of the Proposed Research to the Subjects and Others

There is no direct benefit to participants who enter this study, although some may experience relief from PTSD symptoms, decreased avoidance, decreased conflict, and increased quality of life.

The clinician participants may receive benefit from the training in a new brief family intervention, from access to expert consultation on the intervention, and/or by providing feedback about the potential barriers that require addressing within the mental health clinics. Providers who participate in the treatment portion of the study will receive free training in a new psychotherapy intervention, and this training will also be made available to clinicians who would like the training but do not wish to provide the intervention in the context of the study. Over the longer term, they may also benefit professionally (e.g., future job opportunities at agencies that value family-inclusive approaches to treatment) from the training. Consequently, the potential risks of participation in the study are outweighed by the potential benefit to the participants.

4. Importance of the Knowledge to be Gained

PTSD is a significant public health problem, with national lifetime prevalence rates of 8% (Kessler et al., 1995) and estimated rates in Veterans of the current conflicts in Iraq and Afghanistan of 13-20% (Kok et al., 2012). Family members may serve as a unique resource that can be harnessed to improve outcomes for PTSD treatment; social support is one of the most important predictors of the development and maintenance of

PTSD(Ozer et al., 2008), and family members may provide substantial practical and emotional support for treatment. However, relatives may also inadvertently behave in ways that contribute to the maintenance of the disorder(Erbes et al., 2008). The proposed study will examine a brief family intervention (BFI) delivered in conjunction with individually-delivered trauma-focused treatment.

5. Data Safety and Monitoring Plan (DSMP)

a. Data Monitoring Plan. Data will be collected using standardized forms and will only be identified using the participants' ID number (no names or identifying information will be on the forms). A username and password is required to gain access to the network server, permission is needed to access the data drive, and a separate password is needed to gain access to the database. Data will be stored on a VABHS server (VHABOSCLURES1) and is backed up nightly; no data will be stored on a hard drive.

The codes that link the names of participants and their ID numbers will be kept confidential by the PI in a secured cabinet located within the PI's office (JP campus, room 13B-60) (or, during construction on the 13th floor of Building 1 in JP, in a secure basement storage area appropriate for materials containing PII). Collected data forms will be in a locked file cabinet located in the PI's office (or, during construction on the 13th floor of Building 1 in JP, in a secure basement storage area appropriate for materials containing PII). These data are accessible to the PI and personnel working on the project. Data will be entered electronically by trained staff, and data entry discrepancies will be corrected by the data entry supervisor based on source documents. The quality of the data will be monitored quarterly. Data will be securely transmitted using VA approved methods.

Audio recordings will be captured using Philips recorders with FIPS 140-2 validated encryption. Recordings may be obtained while study staff are teleworking; in these cases the recorders will be stored in the home in a locked cabinet/drawer that is only accessible to the study staff member. Recorders will be hand-carried to the VA as soon as it is feasible and safe to do so, at which point the recordings will be uploaded to the PI's personal research drive behind the VA firewall and deleted from the recording device.

The primary outcomes measures will be CAPS-5 total scores and ratings of homework completion (from the Homework Completion Scale), and number of sessions attended/dropout. Data quality will be monitored by inspection of the completed forms by the research assistant and any problems detected will be discussed with the PI. All assessors will be fully trained on the assessment measures, per the usual training procedures within BSD. Adherence to the intervention will be monitored using recordings of sessions and weekly supervision, as described previously. If diagnostic and/or intervention drift is observed, staff will be retrained until acceptable reliability is reached.

b. Safety Monitoring Plan. In the proposed study we will use the FDA definition of adverse events (AE) and serious adverse events (SAE). Any SAE, whether or not related to the study intervention, will be reported immediately to the IRB. In the event that a participant either withdraws from the study or the PI decides to discontinue a participant due to an SAE, the participant will be monitored by the PI via ongoing status assessment until (a) a resolution is reached (e.g., the problem has resolved or stabilized with no further change expected), (b) the SAE is determined to be clearly unrelated to the study intervention, or (c) the SAE results in death. Outcomes of SAEs will be regularly reported to the IRB. A summary of the SAEs that occurred during the previous year will be included in the annual IRB renewal. Suicidal ideation and AEs will be formally assessed at baseline and at all other assessment visits (see below for detailed information regarding assessment of suicidal ideation).

Participants will be informed that the interim results of the study will not necessarily be revealed to them, even if there is a suggestive trend in favor of the treatment, so as to maintain the scientific integrity of the study(Slutsky & Lavery, 2004). During the first in person screening, potential participants will undergo a comprehensive screening to determine their eligibility for, and safety for, participation in the study. Attention will

be paid to current suicidal ideation. Individuals who report imminent risk will be excluded from participation in the study and will be provided with appropriate clinical referrals.

b.1. Assessment of suicidal ideation: During the course of the study the clinician-administered MINI suicide module will be used to thoroughly assess participant suicidal risk and distress beyond what would be expected in treatment for trauma. The MINI suicide module consists of 9 questions related to suicidal ideation and behaviors, with possible scores ranging from 0 to 53. Low suicide risk is defined as 0-8 points, moderate suicide risk is defined as 9-16 points, and high suicide risk is defined as scoring 17 or greater. The MINI suicide module includes clear guidelines for determining suicide risk, and requires approximately 10 minutes to administer. Individuals will be excluded from enrolling in our proposed trial if they score 17 or higher on the MINI suicide module at the initial assessment. Individuals who are excluded will be provided with appropriate clinical referrals. The PI will follow up with each of these individuals within one week to make sure they have connected with appropriate clinical care.

Additionally, if at any point during the study (either baseline or follow-up) a participant describes a clear intent or inability/unwillingness to develop and follow a Suicide Prevention Safety Plan, which is a VA standard of care, then they will be terminated from the study and the crisis will be managed. Specifically, staff will immediately locate [name], who is a licensed psychologist, or another licensed psychologist, who will follow standard VA suicide prevention and risk management procedures. A licensed clinical psychologist will always be on-site when assessments are conducted. The psychologist will intervene by (a) following up with direct questions about suicidal behaviors, (b) assessing mental status by asking about psychotic symptoms, mood symptoms, and drug and alcohol use, (c) scheduling extra contacts if necessary, emphasizing problem solving, (d) helping the participant to generate short-term objectives, and (e) collaboratively developing or refining a Safety Plan using the VA's comprehensive Safety Planning template and manual. The plan will address what actions need to be taken in the succeeding days to solve the problems that precipitated suicidal behavior. The plan will also address the use of voluntary and involuntary hospitalization, if necessary. In addition to these formal assessments, all participants will be given the number of the on-call psychiatry service at VA Boston Healthcare System and informed that they should call this number after normal business hours in the event that they are feeling suicidal and/or distressed, as well as the National Suicide Prevention hotline number, which is a 24-hour service with a specific line dedicated to Veterans. During business hours the participants will be instructed to contact the PI. Should a participant call to indicate suicidal risk, then the previously described intervention plan will be followed. All Veterans in the study will also be under non-study care through the VABHS, and will be monitored as appropriate by their individual clinicians.

Veteran participants will be administered the MINI-Suicide module at baseline and at each follow-up assessment. Family members will be administered the MINI-Suicide module at the baseline assessment; those family members who score a 0 at baseline on the MINI-Suicide module will not be reassessed at future follow-up points. However, any family members that score ≥ 1 baseline will continue to have the MINI administered at follow-up assessments to monitor risk. If at any point during these follow-up assessments a family member indicates that they are experiencing high levels of suicidal thoughts, study staff will proceed with the steps outlined above (e.g., further assessment by a licensed psychologist of the intensity of thoughts, assessment of any related behaviors, collaborative completion of a Safety Plan, scheduling of additional contacts in the near term, and/or potentially a voluntary or involuntary hospitalization, as determined by the licensed psychologist).

In the event that a participant experiences high distress (i.e. exacerbated symptoms) but without any suicidal ideation or threat, then the PI will intervene by asking direct questions about the nature and causes of the distress, conduct a symptom assessment, and schedule extra contacts (assessments) and/or work closely with the patient's other VA providers if deemed necessary. Veterans' PTSD care will not be constrained or limited in any way by their participation in the study; therefore, their individual clinicians will be free to make any appropriate treatment decisions in response to increased distress, including seeking hospitalization or another higher level of care, discontinuing PE/CPT and instead conducting supportive or crisis-oriented therapy, etc. Any such changes in treatment focus will be monitored and reported to the IRB as appropriate.

DATA ANALYSIS.

Data management: All clinician-administered and self-report questionnaire data will be entered into the database by the Research Assistant (RA) on the same day of administration to ensure completeness. All data will be cleaned and rechecked for accuracy before being exported into the appropriate program (e.g., SPSS, MPlus, and NVivo) for analysis. Data collected via mEMA will be continuously available via the secure cloud-based storage system and accessible via a unique access site available only to study staff.

Overview of data analysis: Quantitative data analysis will be performed using MPlus and SPSS, and NVivo management software will be used for qualitative data. Prior to full data analysis, the balance of randomization will be checked and unbalanced factors between groups will be controlled for in subsequent analyses. Similarly, all major variables will be assessed for skewness and outliers, and in cases where parametric analytic assumptions are violated we will use transformations. Preliminary analyses will consist of descriptive statistics by assessment period. All quantitative outcomes will be tested at a two-sided $\alpha=.05$ level.

Data checking: Standard data checking procedures will include checking forms for missing data, double entry with discrepancy resolution, daily back-up copies of computer files, and examination of key variables for skewness, variability, missing data, and outliers. Data will be transformed to achieve normality if needed. If any outcome variable is too zero-inflated to allow for transformation, it will be analyzed with logistic regression or generalized estimating equation techniques (appropriate for this small pilot study).

Missing data: We will make every effort to retain participants, but as treatment engagement is a key outcome of the present study we will also carefully tabulate and report dropout rates and patterns in the present study, including exact timing of dropout. Multilevel regression models will be used to evaluate treatment outcomes; this approach is robust to missing data and is considered "state of the art" for use with unbalanced data sets due to treatment dropout (Schafer & Graham, 2002). There are also several methods for correcting biases due to missing data when using a multilevel regression approach (e.g., pattern-mixture modeling).

Power analyses: Determining sample sizes for multilevel models is a complex issue and "rules of thumb" are disputed (Maas & Hox, 2005; Mok, 1995). Furthermore, "effective" sample sizes in MLMs (as opposed to nominal sample sizes) will vary according to the model's predictors (Bickel, 2007). Given the aims and scope of this funding mechanism, the present study is considered preliminary. It will provide pilot data to assess the effectiveness of the BFI as well as exploring the proposed mechanisms of action. The use of repeated measures increases our ability to detect significant relationships. Our results will inform next steps in the investigation of the effectiveness and implementation of the BFI, including a fully powered R01 application to examine the BFI in comparison to an established family-based treatment in a routine VA clinic.

Defining key concepts for analyses:

Treatment dropout: Consistent with past trials of CPT and PE, treatment dropout will be defined by ending treatment prior to the allocated treatment period. In the case of CPT full treatment duration is 12 sessions, while in the case of PE full treatment duration is at least 8 sessions and the concomitant agreement of the therapist that an appropriate ending place has been reached. Any Veteran who ends treatment prior to these milestones will be considered a dropout.

Feasibility/Acceptability: In the current study, feasibility and acceptability will refer to the evaluation and analysis of recruitment, randomization, retention, treatment adherence and fidelity, and use of the BFI with the families of Veterans beginning PTSD treatment. These variables help to determine the acceptability of the treatment and procedures for future studies.

Aim 1: Collect qualitative and quantitative data on feasibility and acceptability of the BFI in a routine care setting.

Hypothesis 1: Levels of feasibility and acceptability of the BFI among Veterans, family members, and clinicians will be high and comparable to levels found in the previous efficacy trial in OCD.

Hypothesis 1 analytic strategy: We will examine the feasibility and acceptability of the BFI by examining rates of BFI recruitment and refusal, as well as level of drop-out from the BFI sessions. These data will be benchmarked to previous BFI efficacy data. We will also assess the success of the clinician training program by reviewing rates of clinician recruitment and attitudes reported on the EBPAS-50. Furthermore, we will conduct detailed in-person, semi-structured exit interviews with Veterans, family members, and clinicians in order to collect qualitative data. These data will allow us to contextualize our findings related to the protocol's fit in this novel setting and its acceptability to Veterans, families, and providers. The qualitative interviews will provide more nuanced feedback regarding the perceived fit of the BFI, and further identify necessary modifications to the protocol (see below for qualitative analytic strategy).

Aim 2: Assess the BFI's effects on symptoms as well as potential mechanisms of change using multilevel modeling.

Hypothesis 2a: Veterans whose family members receive the BFI will show lower levels of PTSD symptoms at post-treatment and greater engagement throughout treatment compared to control Veterans.

Hypothesis 2b: Family members who receive the BFI will show more active support for treatment and less accommodation than control family members.

Hypothesis 2c: Family members' active support for treatment will be positively related to Veterans' treatment engagement, and Veterans' levels of perceived criticism will be negatively related to their treatment engagement

Hypothesis 2a-2c analytic strategy: Multilevel regression (i.e., hierarchical linear modeling (HLM), growth curve analysis, etc.) will be used to evaluate change in continuous outcome variables (Singer & Willett, 2003). Multilevel regression is a robust method for analyzing change over time, with excellent options for handling missing data, powerful estimation abilities, and flexibility of modeling. This approach will allow for the analysis of an intent-to-treat sample in line with CONSORT guidelines (Altman et al., 2001). For our analysis of change in the variables of interest we will use a multilevel framework in the Mplus program to model time as a Level 1 predictor of the outcome variables (baseline and weeks 6, 12, and 16). We will first specify an unconditional model to ascertain the shape of the change trajectories (e.g., linear versus quadratic change over Time), and will subsequently specify conditional multilevel models to examine treatment effects and the impact of other variables as predictors of individual differences in change. We will also calculate the Cohen's *d* effect size and 95% confidence intervals in order to provide a benchmark for future trials.

o. Literature Cited

Aarons, G. A., Cafri, G., Lugo, L., & Sawitzky, A. (2010). Expanding the domains of attitudes towards evidence-based practice: The Evidence Based Practice Attitude Scale-50. *Administration and Policy in Mental Health and Mental Health Services Research*, 39(5), 331–340. <http://doi.org/10.1007/s10488-010-0302-3>

Boeding, S. E., Paprocki, C. M., Baucom, D. H., Abramowitz, J. S., Wheaton, M. G., Fabricant, L. E., & Fischer, M. S. (2013). Let me check that for you: symptom accommodation in romantic partners of adults with Obsessive-Compulsive Disorder. *Behaviour Research and Therapy*, 51(6), 316–322. <http://doi.org/10.1016/j.brat.2013.03.002>

Borkovec, T.D., & Nau, S.D. (1972). Credibility of analogue therapy rationales. *Journal of Behavior Therapy and Experimental Psychiatry*, 3, 257-260.

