All Veterans enrolled in the study will be beginning a course of either Prolonged Exposure (PE) or Cognitive Processing Therapy (CPT), which will be delivered as usual by PTSD clinical staff. As the BFI is an adjunctive intervention, Veterans' trauma-focused treatment is considered separate from the present study. The Veterans will be seen by regular clinical staff and no artificial limits will be imposed upon their treatment, although treatment engagement will be tracked (see Assessment section, below). Veterans and their family members will be recruited for the present study at the beginning of a course of treatment at the clinic. Phase I will be an open pilot trial of 4 dyads. All family members in Phase I will receive the BFI, which will be delivered as 2 weekly 50-minute sessions of the BFI, consistent with the application with the BFI in previous work (Thompson-Hollands et al., 2015). Phase II will include 20 dyads (N=40) using identical recruitment, inclusion/exclusion criteria, and assessment structure; however, in this second phase family members will be randomly assigned to receive or not receive the BFI, and VABHS clinicians will deliver the BFI sessions (rather than the PI as in Phase I).

Veterans:

Inclusion criteria.

- (1) has a current diagnosis of PTSD

(2) is 18 years of age or older

(3) has an eligible family member (defined as a spouse/significant other, parent, adult child, sibling, etc., 18 years of age or older who currently has substantial daily or weekly contact with the Veteran)

(4) is beginning a course of either CPT or PE at VA Boston.

Exclusion criteria.

(1) has current diagnoses of unstable bipolar disorder, past or present psychosis, or organic mental disorder

(2) has clear and current suicidal risk (assessed via the MINI-Suicide Module (Sheehan et al., 1998), see Assessment section below)

(3) has current moderate or severe substance use disorder

(4) is currently participating in family-based therapy/couples-counseling

Family members:

Inclusion criteria.

(1) is 18 years of age or older

(2) is the family member (defined as a spouse/significant other, parent, adult child, sibling, etc.) of the Veteran

(3) currently has substantial daily or weekly contact with the Veteran

Exclusion criteria.

(1) has a current diagnosis of PTSD

(2) has current diagnoses of unstable bipolar disorder, past or present psychosis, or organic mental disorder

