(2) has clear and current suicidal risk (assessed via the MINI-Suicide Module (Sheehan et al., 1998), see Assessment section below)

(3) has current moderate or severe substance use disorder

(4) is currently participating in family-based therapy/couples-counseling

Recruitment of Veterans and family members will occur through the VABHS outpatient mental health clinics (e.g., the PTSD Clinic, the Women's Clinic, General Mental Health, Center for Returning Veterans, etc.). All interested participants will be contacted by the PI for a phone screen, where the study and its procedures will be described and a short screen for eligibility will be administered. If the initial screening requirements are met, participants will be invited to an in-person assessment. During the first appointment, the Veteran and family member will be provided with a thorough description of the project and the informed consent form will be reviewed and signed. Baseline assessment measures will then be administered (see Assessment section).

Veterans will proceed with PE or CPT as usual through the clinic, with no restrictions or limitations. Should a Veteran choose to discontinue PE or CPT, he or she will continue to be enrolled in the proposed study for follow-up assessments, as treatment drop-out is a variable of interest. All family members who are to receive the BFI (i.e., all family members in *Phase I* and half of family members in *Phase II*) will participate in the two BFI sessions, and then move into the follow-up portion of the study.

BFI: The BFI is a 2-session individual intervention delivered by a clinician to the adult family member of a Veteran with PTSD who is beginning a course of CPT or PE treatment. The BFI sessions are guided by a manual, which has previously been developed by the PI but will

be revised for the purposes of the current study as described earlier to enhance its relevance to the families of Veterans with PTSD. The BFI may be completed either in person or remotely via telephone.

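### Therapy type (PE or CPT) is part of the sessions/dropout outcome, yet it is neither a described stratification factor nor a prespecified covariate in Phase II

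*Combined protocol and SAP*

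**What the plan says.** **Allocation.** Section (4) Work Proposed states "Phase II will include 20 dyads (N=40") and that "in this second phase family members will be randomly assigned to receive or not receive the BFI". Later in that section, the BFI goes to "half of family members in" Phase II, which implies 10 dyads per arm. No stratification factor, blocking or minimisation is described.

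**Therapy type.** A Veteran qualifies only if he or she "is beginning a course of either CPT or PE at VA Boston", so PE or CPT is known at entry.

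**Outcome.** The Data Monitoring Plan (section 5a) lists as primary outcomes the CAPS-5 total, homework ratings and "number of sessions attended/dropout". Under Defining key concepts for analyses, "CPT full treatment duration is 12 sessions, while in the case of PE full treatment duration is at least 8 sessions", and PE also needs the therapist's agreement that a suitable end point has been reached. Stopping before the milestone for one's own therapy counts as dropout.

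**Adjustment.** The Overview of data analysis says "the balance of randomization will be checked and unbalanced factors between groups will be controlled for in subsequent analyses". It names no factors, test or threshold. The Hypothesis 2a-2c analytic strategy names time, treatment and further predictors it does not identify. Therapy type is not among the named terms.

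**The concern.** A Veteran who stops at session 9 is a dropout in CPT but may be a completer in PE. A completed PE course may also be shorter than a completed CPT course. If one arm happens to hold more PE Veterans, part of the difference in sessions attended can reflect therapy mix and not the BFI. If the arms are balanced on therapy, any PE/CPT difference stays in the residual and widens the interval.

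The only stated route to adjustment is a balance check made after allocation. It leaves open whether therapy type is looked at and how uneven a split must be before it is adjusted for, so the analysis model is not fixed in advance. This matters even in a pilot: outcomes are tested at two-sided 0.05, and Cohen's d with a 95% interval is to serve as a yardstick for a later, fully powered trial.

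**Working it through.** The plan gives no power, SD or effect size for this trial, so there is no figure of that kind to reproduce. The headcount is consistent: 4 + 20 = 24 dyads, or 48 people.

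**Inputs from the plan:** 20 randomised dyads, 10 per arm; full course of 12 sessions for CPT and a minimum of 8 for PE; two-sided alpha 0.05.

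**Assumptions, not in the plan:** number K of Veterans starting PE, 5 to 15; mean gap between therapies in sessions attended, 0 to 4 (12 − 8 = 4 if PE stops at its minimum); within-therapy SD 3 sessions; true BFI effect 3 sessions.

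**1. Chance imbalance.** With 10 v 10 fixed, the number of PE Veterans in one arm is hypergeometric(20, K, 10). For K = 10, the probability of 7 v 3 or worse is 2 × (14,400 + 2,025 + 100 + 1) / 184,756 = 0.179. Probability that the PE counts differ by 4 or more:

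| K starting PE | Probability |
|---|---|
| 5 or 15 | 3.3% |
| 6 or 14 | 14.1% |
| 7 or 13 | 5.7% |
| 8 or 12 | 17.0% |
| 9 or 11 | 7.0% |
| 10 | 17.9% |

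For odd K the difference is itself odd, so 4 or more means 5 or more; this is why those rows are lower. The range is 3% to 18%.

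**2. Would a balance check notice?** The plan gives no criterion. If it were a 5% Fisher exact test with K = 10, 7 v 3 gives p = 0.18 and is not flagged; 8 v 2 gives p = 0.023 and is.

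**3. Shift in the sessions difference with no BFI effect.** Shift = difference in PE share × gap. For 7 v 3 the share difference is 0.7 − 0.3 = 0.4, giving 0, 0.8 and 1.6 sessions at gaps of 0, 2 and 4.

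**4. Precision and power.** With half on each therapy and arms balanced on it, unadjusted variance = 3² + 0.25 × gap² and adjusted variance = 3² = 9. SE = SD × √(2/10). Power is from the noncentral t, with 18 df unadjusted and 17 adjusted. This two-group comparison of session counts stands in for the growth model.

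| Gap | Unadjusted variance | Therapy share of variance | SE unadjusted | SE adjusted | Power unadjusted | Power adjusted |
|---|---|---|---|---|---|---|
| 0 | 9 | 0% | 1.34 | 1.34 | 56% | 56% |
| 1 | 9.25 | 3% | 1.36 | 1.34 | 55% | 56% |
| 2 | 10 | 10% | 1.41 | 1.34 | 52% | 56% |
| 4 | 13 | 31% | 1.61 | 1.34 | 42% | 56% |

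The gain also depends on the SD. At a gap of 4, the ratio of unadjusted to adjusted variance is (4 + 4)/4 = 2.00 for SD 2, 13/9 = 1.44 for SD 3 and (16 + 4)/16 = 1.25 for SD 4.

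**The case against.** **The size of the therapy difference is unknown.** PE's 8 sessions is a floor, and section (4) places no limits on treatment, so PE courses may run as long as CPT courses or longer. This stands: the gain can be nil, and the 4-session row is the largest case shown. A reader might take 12 against 8 as an established 4-session difference; the documents do not support that.

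**The balance check may already deal with it.** A 6 v 4 or 7 v 3 split could be judged unbalanced and adjusted for, and the model text leaves room for further predictors. This stands in part. It cannot be said that the plan leaves such splits unadjusted, only that it does not say. Nor does the check call for adjustment when the arms balance, which is when the precision argument applies.

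**Dropout is already judged against each therapy's own milestone, and the plan does not show that dropout rates differ by therapy.** Correct. The numerical case here rests on session counts. At the upper dropout figure in section (1), 36%, about 7 of 20 Veterans would drop out (0.36 × 20 = 7.2), and another covariate in a binary model risks sparse cells.

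**The cost is not always one degree of freedom.** A growth model may also need a therapy-by-time term. In a 7 v 3 split with K = 10, the arm-therapy correlation is 0.4, so the adjusted SE rises by a factor of 1/√(1 − 0.4²) = 1.09 before any reduction in residual variance. That is the price of removing the shift in step 3.

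**This is a preliminary study with no power claim.** True, and so the point concerns how the estimate can be interpreted, not a missed power target.

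**Conclusion.** The concern holds for one of the three listed primary outcomes, sessions attended/dropout. Therapy type is known at entry and is built into that outcome's definition, yet its place in the analysis is left to an unspecified check.

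The consequence is chance error and lost precision. A reader might infer a biased BFI estimate, but random assignment keeps it unbiased on average. A reader might also extend the point to homework ratings or the CAPS-5; no section says that either differs by therapy.

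The size rests on assumptions the documents cannot settle. A PE difference of 4 or more between arms has probability 3% to 18%, depending on the unstated therapy mix. A 7 v 3 split shifts the sessions difference by 0 to 1.6. At SD 3 and a 3-session effect, the power gain from adjustment runs from nothing to 14 points (56 − 42). The change is still worth making: it fixes the model in advance at little cost.

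**What to change.** In the Overview of data analysis and the Hypothesis 2a-2c analytic strategy, state that therapy type at entry (PE v CPT) is a fixed covariate in the Phase II models for the continuous Hypothesis 2a outcomes, whatever the balance check shows. Report sessions attended and dropout by therapy type as well as overall. Do not require the covariate in the binary dropout model, where events are few.

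**Cost:** about one degree of freedom (18 to 17 in the simple comparison) and one item already known at entry. If the therapies do not differ and the arms are balanced on therapy, the power loss is negligible (56% either way).

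Stratifying the randomisation by therapy is optional, and relevant only if Phase II randomisation has not started. The document is dated July 2021 and expected enrolment from winter 2016/2017, so that may no longer be open; the analysis change does not depend on it.
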